8.3 Drug Product Supply, Administration and Inventory

8.3.1 Handling

Qualified personnel, familiar with procedures that minimize undue exposure to themselves and the environment, should undertake the preparation, handling, and safe disposal of the chemotherapeutic agent in a self-contained and protective environment.

8.3.2 Availability

ONC201 is provided by the Sponsor. A sufficient quantity of study supplies will be supplied to the investigator (or qualified designee) at each study center by the Sponsor or Sponsor-authorized depot. Once received at the study center, ONC201 should be stored in accordance with the storage conditions, in a securely locked area, with limited access to authorized site staff.

Only patients enrolled in the study may receive study drug and only authorized site staff may prepare, supply, or administer study drug.

If a subject cannot physically visit a study site, the site may choose to ship the study drug direct to the patient. Upon patient consent and regulatory approval, investigational product may be delivered to his/her designated location (e.g., home, office) via a Chimerix approved direct to patient courier service. Study drug pick up and delivery must be arranged by the study site with the direct to patient courier service. In compliance with data privacy regulations, the vendor has a data privacy system in place to cover any local obligations.

8.3.3 Administration

Patients will receive ONC201 while in the clinic for C1D1. Patients can take medications at home for other dosing. The study drug, ONC201, will be supplied in capsule form for oral dosing.

Study patient will receive a 3-week supply of ONC201 during office visit for the first 6 cycles (not applicable to Arm A, which is closed). After the first 6 cycles, the Investigator can prescribe a supply up to 10-weeks beyond the first 6 cycles considering an allowed 10-day window for repeating MRI every 8 weeks.

Patients should take the dose of ONC201 specified by their physician 2 hours prior or 2 hours following food or a meal. If the patient vomits after taking ONC201, they should not retake the dose. Missed doses will not be made up, if more than 3 days from the intended day of administration.

ONC201 should be taken with a glass of water and consumed over as short a time as

possible. Patients should swallow the capsules as a whole and not chew them. Do not crush or empty the capsule. If vomiting occurs during the course of treatment, no re-dosing of the patient is allowed before the next scheduled dose. The occurrence and frequency of any vomiting during a treatment cycle must be noted as an adverse event.

8.3.4 Accountability

The investigator (or qualified designee) is responsible for ensuring adequate accountability of all used and unused study drug. This includes acknowledgment of receipt of the shipment(s) of study drug (date, quantity, and condition), participant dispensing records, and returned or destroyed capsules. Dispensing records will document the dispensing of the study drug to individual participants (including date dispensed, and participant identifier number), the initials of the person(s) dispensing the study drug, and the return and/or disposal of the study drug. All study drug records must be maintained at the site and copies must be submitted to the Sponsor at the end of the study.

8.3.5 Destruction and Return

After verification of the study drug records by the study monitor, all remaining study drug supplies should be destroyed according to directions provided by the Sponsor (or its designee) and/or any applicable site-specific standard operating procedures. If necessary, unused study drug supplies may be returned to the appropriate depot with prior approval from the Sponsor (or its designee). If study drug is approved for onsite destruction by the Sponsor, the investigator must maintain accurate records for all study drug destroyed. Records must show the identification and quantity of each unit destroyed, the method of destruction, and person who disposed of the drug.

9. BIOMARKER, CORRELATIVE, AND SPECIAL STUDIES

9.1 Pharmacodynamic Studies

As part of this study we will retrieve archived tumor tissue samples at the time of enrollment for subjects enrolled in this study to conduct future correlative assays to measure biomarkers of therapeutic response to ONC201 including molecular markers involved in the mechanism of action of ONC201. The mechanism of action of ONC201 appears to alter the expression or phosphorylation of several proteins involved in cell signaling pathways that govern tumor cell survival and cell death. To assay such changes, serum samples will be obtained for subsequent analysis of pharmacodynamic effects of ONC201.

One tube of blood for serum PD samples will be taken at baseline on Day 1 of Cycle 1 (prior to ONC201 dosing), and again on Day 2 and 8 of Cycle 1, then again at pre-dose on subsequent cycles, and at the follow-up visit at the end of treatment, for correlative studies.

To obtain serum, one (1) tube of 6 mL of peripheral blood will be collected without anticoagulant. The sample will be allowed to clot, and serum will be harvested by iterative centrifugation. Serum will be divided into 2-3 mL aliquots and stored cryogenically. Detailed procedures and supplies are described in the lab manual associated with this protocol.

Archival tumor assessments of cell signaling pathways that are associated with ONC201 will be conducted on tissue obtained from participants. If available, a minimum of 1 formalin-fixed paraffin-embedded (FFPE) archival tumor tissue block (preferred) or a minimum of 10 FFPE unstained sections from most recent pre-registration biopsy/surgery are to be submitted within 60 days of registration.

For patients in Arm C and E, both archival as well as freshly resected tumor tissue will be collected. The tumor may be resected using neuronavigation or intraoperative MRI, enabling resection of enhancing tumor and resection or biopsy of non-enhancing tumor. Surgical resection of the non-enhancing lesions should be performed only in the non-eloquent areas that show FLAIR changes on MRI. Tissue may be collected from both the enhancing core and non-enhancing edge of individual tumors. Tissue should be separated into enhancing and non-enhancing specimens. Tissue will then be divided into four samples. The diameter of tissue will be approximately 0.3 to 0.5 cm for each of the 4 pieces of the tumor that will be preserved. Three will be flash frozen for RNA, DNA, protein, and drug concentration analyses. The fourth sample will be formalin-fixed and paraffin-embedded tissue blocks will be prepared for immunohistochemistry. If possible, a cross section of the resected tissue spanning the tumor and normal margins is requested for the formalin-fixed specimen. The tissue will be assayed for the following markers that have been implicated in the mechanism of action of ONC201 such as DRD2, DRD5, TGM2, KSR1, ATF4, CHOP, pAkt, pERK, TRAIL, and DR5 ([Allen 2013a](#); [Ishizawa 2016](#); [Kline 2016](#)).

Please refer to the study laboratory manual for shipping instructions.

9.2 ONC201 Plasma Concentration

For each patient, one (1) EDTA tube of 6 mL of blood will be collected in EDTA tubes at baseline on Day 1 of Cycle 1 (prior to ONC201 dosing), and again 2 hours (\pm 15 minutes) following the first dose of ONC201, and then not again until the follow-up visit at the end of treatment. All samples will be processed to produce plasma that will be stored cryogenically until analysis. A detailed procedure is provided in the lab manual.

10. STUDY CALENDAR

Study visits and procedures may be scheduled with a ± 3 business day window except for the Screening visit and neuroimaging (contrast-enhanced CT or MRI) (± 7 days). One **Treatment Cycle** is defined as 3 weeks (21 days). One **Evaluation Cycle** is defined as 8 weeks (56 days ± 7 days). ONC201 will be administered every 3 weeks for patients in Arm A and every week for patients in Arm B, C, D, E, and F.

	Screening / Baseline	CXD1 (All Arms)	D2C1 for All Arms	D8C1 for All Arms	D15C1 for Arms C and E only ¹⁰	Unscheduled visit, or brain surgery	Evaluation Cycles	End of Treatment / Follow-up
	Within 28 days of Treatment	(21 \pm 3 days) ¹⁴					Every 8 weeks (56 \pm 7 days)	(30 \pm 3 days post last dose)
Medical/RX history, including prior CT/MRI scans ¹¹	X							
Physical exam, Neurologic exam, KPS, Height, weight ¹	X	X			X	X		X
Vital signs ²	X	X			X	X		X
12-lead ECG	X	X			X	X		X
Hematology ³	X	X			X	X		X
Full serum chemistries ³	X	X			X	X		X
MDASI questionnaire	X	X						X
Coagulation tests	X							X
Pregnancy test ⁴	X							X
Disease assessment ⁵	X						X	X
Screening brain/spine CT/MRI ¹⁰	X							
AEs ¹²		→						
Con-meds		→						
Blood sample for ONC201 plasma concentration		X ⁷						X
Fresh tumor tissue ¹³					X	X		
Blood sample for PD		X ⁸	X ⁸	X ⁸				X
Disease status and survival ⁶								X
Archival tumor tissue	X ⁹							

1. Determine if significant weight loss or gain ($\pm 10\%$). Abbreviated PE on Day 1 of each treatment cycle or as clinically indicated. Neurological assessments will use the NANO scale.
2. Vital signs: systolic and diastolic blood pressure, respiration, pulse, oral temperature prior to treatment on day 1 of each cycle. Vitals will also be required 2 hours after dosing for day 1 of cycles 1 and 2.
3. Obtain and review prior to each dose of ONC201 on Day 1 of each subsequent cycle, or more frequently if clinically indicated.
4. Pregnancy Test – baseline within 7 days of start of treatment and at end of study - urine or serum in women of child-bearing potential. A female of childbearing potential is a sexually mature woman who: 1) has not undergone a hysterectomy or bilateral oophorectomy; or 2) has not been naturally postmenopausal for at least 24 consecutive months (i.e., has had menses at any time in the preceding 24 consecutive months).
5. Neuroimaging (disease assessments) must be taken within 7 days prior to physician visit. Disease assessments will be performed at 8 weeks and then every 8 weeks (± 7 days) thereafter until patients come offstudy. Every month via telephone for all subjects for 1 year.
7. Obtain blood sample for cycle 1 day 1 only at baseline prior to ONC201 dosing and again at 2 hours (± 15 minutes) post-administration of ONC201.
8. Obtain blood sample for PD pre-dose on day 1 of cycle 1, Day 2, and pre-dose on Day 8 of cycle 1. For cycles 2 and beyond, only pre-dose blood samples on day 1 of each cycle will be collected.
9. Obtain archival tumor tissue (if available) at the time of enrollment, in accordance with the laboratory manual. For Arm C and E, patients must be clinically evaluated prior taking the dose immediately following surgery. Typically surgery will occur 24 hours after the second dose of treatment, meaning that for day 15 of cycle 1 (ie, the dose following surgery), patients will be evaluated prior to taking this dose. Drug may be taken at home after this assessment. However, if surgery is not planned to occur until after the third dose of treatment, subjects will not be required to have an evaluation on day 15 of cycle 1. The dose immediately following surgery would fall on day 1 of cycle 2, a day where all patients are required to come into clinic for clinical and laboratory assessment.
10. Baseline brain MRI, with and without contrast is required within 14 days from C1D1. Brain CT is acceptable for patients who are not able to conduct MRI scans. Entire MRI scans with and without contrast is required for patients to be screened for arms D and F.
11. Provide imaging files and assessments from initial diagnosis, surgery planning, post-surgical, post chemoradiation, scheduled and unscheduled MRIs.
12. The safety follow-up period lasts until 30 days after discontinuation of study treatment or date initiation of a new anticancer therapy after discontinuation of ONC201.
13. Fresh tumor tissue to be collected for both arm C and E from surgery occurring prior to C1D15 (timing may vary depending on surgical schedule and other factors without being considered a protocol deviation). Fresh tumor collection may be obtained from unscheduled brain tumor surgery while patient is on active treatment and until 30 days from last ONC201 dose.
14. If a patient completes 6 cycles the patient may be seen every 8 weeks for routine assessment of physical exam, and AE/concomitant medication assessment.

11. MEASUREMENT OF EFFECT

After signing informed consent patients will undergo screening procedures including baseline radiologic imaging by contrast-enhanced CT scan or MRI within 14 days prior to initiating study drugs.

Patients who remain on study will have tumor assessments performed at 8 weeks (± 1 week) after initiation of therapy and then every 8 weeks (± 1 week) thereafter. In addition to reassessment scans, confirmatory scans should also be obtained not less than 4 weeks following initial documentation of objective response. To be assigned a status of PR or CR changes in tumor measurements must be confirmed by repeat assessments that should be performed no less than 4 weeks after the criteria for response are first met.

Efficacy will be assessed by the RANO response criteria as noted below. RANO-HGG and RANO-LGG will be used for each evaluation to assess contrast-enhancing lesions and T2/FLAIR hyper-intense lesions, respectively.

11.1 Definitions

Evaluable for Efficacy and Safety

Patients who have received at least one dose of study drug will be considered evaluable for efficacy and safety. These patients will have response classified according to the definitions stated below.

Evaluable for Intratumoral Concentrations

Patients in Arms C and E must have sufficient tumor tissue from biopsy to permit quantitation of intratumoral concentrations of ONC201 to be considered evaluable for these arms. Patients found to have insufficient tissue may continue treatment, but will be replaced.

Evaluable Non-Target Disease Response

Patients who have lesions present at baseline that are evaluable but do not meet the definitions of measurable disease ($a+b > 10\text{mm}$), have received at least one cycle of therapy, and have had their disease re-evaluated will be considered evaluable for nontarget disease. The response assessment is based on the presence, absence, or unequivocal progression of the lesions.

Disease Parameters

For the purposes of this study, patients should be reevaluated for response at 8 weeks of therapy and then every 8 weeks thereafter. In addition to baseline scan(s), confirmatory scans should also be obtained not less than 4 weeks following initial documentation of objective response.

ORR by RANO-HGG is defined as the proportion of subjects in the analysis population who have confirmed complete response (CR) or partial response (PR) using RANO-HGG criteria. Radiographic assessments will be performed by the investigator for the primary endpoint, but may also be separately assessed by blinded independent central review. Duration of response

is defined as time from first RANO-HGG response (only if confirmed) to disease progression in subjects who achieve a PR or better.

ORR by RANO-LGG is defined as the proportion of subjects in the analysis population who have confirmed CR, PR, or minor response (MR) using RANO-LGG criteria determined by the investigator (but may be separately assessed by blinded independent central review). Duration of response is defined as time from first RANO-LGG response (only if confirmed) to disease progression in subjects who achieve a MR or better.

11.2 Disease Parameters

Measurable Disease

Bi-dimensionally, contrast-enhancing, measurable lesions with clearly defined margins by CT or MRI scan, with a minimal diameter of 1 cm, and visible on 2 axial slices which are at least 5 mm apart with 0 mm skip. Measurement of tumor around a cyst or surgical cavity, if necessary, requires a minimum thickness of 3 mm. If there are too many measurable lesions to measure at each evaluation, the investigator must choose the largest two to be followed before a participant is entered on study. The remaining lesions will be considered non-measurable for the purpose of objective response determination. Unless progression is observed, objective response can only be determined when all measurable and non-measurable lesions are assessed.

Non-Measurable Evaluable Disease

Unidimensionally measurable lesions, masses with margins not clearly defined, lesions with maximal diameter < 1cm.

11.3 Response/Progression Categories

The modified RANO Response Criteria to be used in this study are summarized below. If changes in the primary field lesions lead to assessment of progressive disease, this assessment must be confirmed at least 4 weeks later.

11.3.1 Complete response (CR). All of the following criteria must be met:

- a) Complete disappearance of all enhancing measurable and non-measurable disease sustained for at least 4 weeks. In the absence of a confirming scan at least 4 weeks later, this scan will be considered only stable disease.
- b) No new lesions.
- c) All measurable and non-measurable lesions must be assessed using the same techniques as baseline.
- d) Participants must be on no steroids or on physiologic replacement doses only.
- e) Stable or improved non-enhancing (T2/FLAIR) lesions.
- f) Stable or improved clinically, for clinical signs and symptoms present at baseline and recorded to be disease related.

Participants with non-measurable disease cannot have a complete response. The best response possible is stable disease.

11.3.2 Partial response (PR). All of the following criteria must be met:

- a) Greater than or equal to 50% decrease compared to baseline in the sum of products of perpendicular diameters of all measurable enhancing lesions sustained for at least 4 weeks. In the absence of a confirming scan at least 4 weeks later, this scan will be considered only stable disease.
- b) No progression of non-measurable disease.
- c) No new lesions.
- d) All measurable and non-measurable lesions must be assessed using the same techniques as baseline.
- e) The steroid dose at the time of the scan evaluation should be no greater than the dose at time of baseline scan.
- f) Stable or improved non-enhancing (T2/FLAIR) lesions on same or lower dose of corticosteroids compared to baseline scan.
- g) Stable or improved, for clinical signs and symptoms present at baseline and recorded to be disease related clinically.

Participants with non-measurable disease cannot have a partial response. The best response possible is stable disease.

11.3.3 Progressive disease (PD).

Any of the following criterion must be met:

- a) > 25% increase in sum of the products of perpendicular diameters of enhancing lesions (over best response or baseline if no decrease) on stable or increasing doses of corticosteroids.
- b) Any new enhancing measurable lesion.
- c) Clear clinical deterioration not attributable to other causes apart from the tumor (e.g., seizures, medication side effects, complications of therapy, cerebrovascular events, infection, etc.). The definition of clinical deterioration is left to the discretion of the investigator but it is recommended that a decline in the Karnofsky Performance Score (KPS) from 100 or 90 to 70 or less, a decline in KPS of at least 20 from 80 or less, or a decline in KPS from any baseline to 50 or less, for at least 7 days, be considered neurologic deterioration, unless attributable to co-morbid events or changes in corticosteroid dose.
- d) Failure to return for evaluation due to death or deteriorating condition.

11.3.4 Minor Response (MR).

Apply to T2/FLAIR hyper-intense lesions only. All of the following criteria must be met:

- a) 25–50% reduction in perpendicular diameters of lesion
- b) No new lesions.
- c) The steroid dose at the time of the scan evaluation should be no greater than the dose at time of baseline scan.
- d) Stable or improved, for clinical signs and symptoms present at baseline and recorded to be disease related clinically.

11.3.5 Stable disease (SD).

All of the following criteria must be met:

- a) Does not qualify for CR, PR, or progression.
- b) All measurable and non-measurable sites must be assessed using the same techniques as baseline.
- c) Stable clinically.

11.3.6 Unknown response status.

Progressive disease has not been documented and one or more measurable or non-measurable lesions have not been assessed.

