5. TREATMENT PLAN

5.1 Treatment Regimen

One cycle is defined as three weeks. ONC201 will be provided as an oral capsule at a strength of 125mg per capsule (alternative strengths may be manufactured). For patients enrolled in Arm A, treatment with ONC201 will be administered once every three weeks in the clinic at the RP2D of 625mg.

For patients in Arm B, C, D, E, and F, ONC201 will be administered weekly (i.e., days 1, 8, and 15 of each cycle) at the RP2D of 625mg. For all participants, C1D1 dose will be taken in clinic. All other doses may be taken at home.

For Arm C and E, subjects must be evaluated prior to dosing for the first dose after surgery (i.e. the dose that would occur approximately one week post-surgery). For Arm C and E, ONC201 initiation will be scheduled so that surgical resection will be performed approximately 24 hours after at least the second dose of ONC201 (6 patients for each arm).

If it is not possible to coordinate the timing on the surgery and administration of ONC201 on consecutive days, deviation from this timing is permitted. For Arm C and E, patients will continue weekly dosing one week after surgical resection if the patient is deemed by the treating physician to be sufficiently recovered from surgery; patients requiring a delay of >3 weeks should go off protocol therapy. Arm C and E participants will be required to undergo pretreatment evaluation (to include vitals, physical examination, laboratories), prior to dosing for this day (i.e. if surgery occurs 24 hours after cycle 1 day 8, patients will be required to undergo clinical and laboratory evaluation on cycle 1 day 15). This dose may still be taken at home after the clinical evaluation. Patients in Arm C and E who after surgery are found to have insufficient resected tumor tissue for correlative studies will continue on treatment but will not count towards accrual of Arm C or E.

ONC201 should be taken with a glass of water and consumed over as short a time as possible. Patients should swallow the capsules as a whole and not chew them. Do not crush or empty the capsule. If vomiting occurs during the course of treatment, no re-dosing of the patient is allowed before the next scheduled dose. The occurrence and frequency of any vomiting during an ONC201 treatment must be noted as an adverse event (AE).

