#### 2. General Conventions

The All Treated Analysis Set includes all patients who receive at least one dose of ONC201. This will be used for all analyses.

Unless otherwise specified, continuous variables will be summarized using descriptive statistics [number of observations, mean, standard deviation (SD), median,  $1^{st}(Q1)$  and  $3^{rd}(Q3)$  quartiles, minimum and maximum]. Categorical variables will be summarized as number (percent) of patients.

Day 1 is defined as the date of the first dose of study drug. For events that occur on or after Day 1, study day is defined as (date of event - date of Day 1 + 1). For events that occur prior to Day 1, study day is defined as (date of event - date of Day 1). There is no Day 0. Baseline is defined as the last observed measurement on or before the date of the first dose of study drug.

In general, other than for partial dates, missing data will not be imputed and will be treated as missing. Unless otherwise specified, partial dates will be imputed using the following rules:

- If year is missing, do not impute.
- If only day is missing, impute day as 1st of the month for start dates, end of the month for end dates, and 15th of the month for other dates.
- If day and month are missing, impute as January 1st for start dates, December 31st for end dates, and July 1st for other dates.

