#### 3. Analyses

All analyses will be presented by Arm and for All Patients. Otherwise, specified patient disposition, study drug usage, prior/concomitant/post-ONC201 medications, demographic and baseline characteristics, adverse events, and laboratories will use methods and summaries defined in the ISS SAP.

Laboratory boxplots will be presented for all tests with at least 60 patients having numeric baseline results: one plot per test, time on the x-axis, value on the y-axis. The plots will not be broken out by arm (i.e. only the All Patients group). Only Baseline and Cycles 2-12 will be presented. For Cycles 2-12, nominal visits will be used; if multiple values are associated with a visit, the highest value will be used for chemistry tests and lowest value will be used for hematology tests.

The following efficacy analyses will be performed: best overall response, overall response rate, disease control rate, duration of response, progression-free survival, and overall survival. All analyses will be

based on the investigator-assessed overall RANO response. Discontinuation of treatment due to progressive disease will also be considered. All analyses, aside from overall survival, will be censored at the earlier of: (1) last disease assessment or (2) initiation of other anticancer therapy.

Cycle 1, 2 hour ONC201 plasma concentrations will be summarized descriptively.

Collected data contributing to presented tables and figures will be listed.

Other analyses specified in the protocol will either not be completed, or will be defined outside the scope of this plan.

Following is a complete list of the tables, figures, and listings to be prepared (with clarifying notes in parentheses).

Number	Description
Table 1.1	Patient Disposition
Table 1.2	Demographics and Baseline Characteristics
Table 1.3	Study Drug Usage
Table 1.4.1	Prior Medications
Table 1.4.2	Concomitant Medications
Table 1.4.3	Post-ONC201 Medications
Table/Figure 2.1	Progression-free Survival
Table/Figure 2.2	Overall Survival
Table 2.3	Response Rate (includes ORR, BOR, and DCR)
Table/Figure 2.4	Duration of Response
Table 3.x.1*	Treatment-emergent Adverse Events (TEAE)
Table 3.x.2*	TEAE Grade 3 and Above
Table 3.x.3*	Serious TEAE
Table 3.x.4*	TEAE Leading to Death
Table 3.x.5*	TEAE Leading to Study Drug Discontinuation, Reduction, or Interruption
Table 3.x.6*	Study Drug Related TEAE
Table 3.x.7*	Study Drug Related TEAE Grade 3 and Above
Table 3.x.8*	Study Drug Related Serious TEAE

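### In Arms C and E no rule stops a reduction produced by the planned resection from counting as a RANO response, and the SAP pools it into All Patients

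*Protocol*

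**What the plan says.** **Reference scan.** Protocol Section 11 requires "baseline radiologic imaging by contrast-enhanced CT scan or MRI within 14 days prior to initiating study drugs". SAP Section 2 adds a general rule without an arm exception: "Baseline is defined as the last observed measurement on or before the date of the first dose of study drug".

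**Response.** Protocol Section 11.3.2 defines the PR size condition as "Greater than or equal to 50% decrease compared to baseline in the sum of products of perpendicular diameters of all measurable enhancing lesions", held for at least 4 weeks. The remaining PR conditions concern non-measurable disease, new lesions, imaging technique, steroid dose, T2/FLAIR findings and clinical status. Section 11.3.1 defines complete response (CR) as disappearance of enhancing disease, also confirmed at 4 weeks. That is an absolute state, not a percentage of baseline.

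**Surgery.** Protocol Section 5.1 schedules Arms C and E so that "surgical resection will be performed approximately 24 hours after at least the second dose of ONC201". The footnotes to the Section 10 calendar say: "Typically surgery will occur 24 hours after the second dose of treatment". Before the first dose after surgery, Section 5.1 says these patients are "required to undergo pretreatment evaluation (to include vitals, physical examination, laboratories), prior to dosing for this day". That list contains no imaging. The calendar marks disease assessment only at screening, every 8 weeks and at end of treatment.

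**Reporting.** SAP Section 3 makes the efficacy analyses "based on the investigator-assessed overall RANO response" and states: "All analyses will be presented by Arm and for All Patients". SAP Section 2 applies the All Treated set to every analysis.

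**The concern.** An ORR is read as tumor shrinkage under the drug. In Arms C and E an operation falls between the reference scan and the first scheduled response scan. Protocol Section 9.1 describes resection of enhancing tumor, which is the tissue that the PR criterion measures. If the resection removes at least half the measurable enhancing area and the other conditions are met, the text records a response that may owe nothing to the drug.

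The by-arm rows at least let a reader see that Arms C and E are surgical arms. The All Patients column does not. ORR, best overall response (BOR) and duration of response (DoR) could then carry a surgical contribution that cannot be separated out. The same would apply to an Arm D analysis if patients with a known H3 K27M mutation from other arms were added to it, as Protocol Section 13.1 permits.

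**Working it through.** The plan gives no figure on this point, so there is none to reproduce. The check traces the sequence of events and then sizes the effect.

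**1. Sequence in a typical Arm C or E patient.**
- Reference scan: 0–14 days before first dose (Protocol Sections 3.1 and 11).
- Second weekly dose: cycle 1 day 8, which is 7 days after initiation. Surgery follows about 24 hours later, so about 8 days after initiation.
- First scheduled response scan: 56 ± 7 days (Protocol Section 5.3).
- Gap from surgery to that scan: 56 − 8 = 48, ± 7, so 41–55 days.

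The reference scan always precedes the planned surgery, and no scan between surgery and week 8 is scheduled to replace it.

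**2. A lesion with no drug effect (sizes assumed).** Baseline 40 × 30 = 1,200 mm². Residual after surgery 25 × 20 = 500 mm².
- Change from the documents' baseline: 1 − 500/1,200 = 58% decrease, which meets the PR size condition.
- Change from a post-operative reference: 0%, stable disease.
- If the residual then grows 20% to 600 mm², the change from baseline is 1 − 600/1,200 = 50% decrease, still at the PR threshold.

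**3. Arm sizes (Protocol Sections 1.1 and 13.1).**
- Arm C: 6 with sufficient tissue, up to 12 enrolled. Arm E: 12 with sufficient tissue, up to 18 enrolled. Section 5.1 gives 6 for each surgical arm; the Section 13.1 figure of 12 for Arm E is used here.
- Operated patients: 6 + 12 = 18, up to 12 + 18 = 30. Patients with insufficient tissue are identified only after surgery, so they count as operated.
- Arms A, B, D and F: 4 × 16 = 64 to 4 × 30 = 120.
- All Patients: 64 + 18 = 82 to 120 + 30 = 150.

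**4. Effect of one surgery-driven response on ORR, assuming that everyone has measurable disease.**
- Arm C: 1/12 = 8.3% to 1/6 = 16.7%.
- Arm E: 1/18 = 5.6% to 1/12 = 8.3%.
- All Patients: 1/150 = 0.67% to 1/82 = 1.22%.

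Protocol Section 13.3 leaves patients without measurable disease out of ORR. If only 80% were measurable (assumption), the pooled step would be 1/120 = 0.8% to 1/66 = 1.5%.

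**5. Illustration of the pooled column.** Let p be the ORR without any surgical contribution, q the share of operated patients who meet PR through surgery, and s the operated share of All Patients. Then pooled ORR = p + (1 − p) × q × s. The documents give neither p nor q; p = 5% and q = 25–75% are assumptions.

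| Operated / other / total | s | q = 25% | q = 50% | q = 75% |
|---|---|---|---|---|
| 18 / 120 / 138 | 13.0% | 8.1% | 11.2% | 14.3% |
| 30 / 120 / 150 | 20.0% | 9.8% | 14.5% | 19.3% |
| 18 / 64 / 82 | 22.0% | 10.2% | 15.4% | 20.6% |
| 30 / 64 / 94 | 31.9% | 12.6% | 20.2% | 27.7% |

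The extremes are 0.05 + 0.95 × 0.25 × 0.1304 = 0.081 and 0.05 + 0.95 × 0.75 × 0.3191 = 0.277. With q = 0 the pooled ORR stays at 5%.

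**The case against.** **Frequency is unknown.** A reader might infer that responses in Arms C and E will mostly be surgical. The documents do not support that. They state no extent of resection. Section 9.1 asks for four small tissue pieces and allows biopsy of non-enhancing tumor, and Section 11.1 refers to tissue from biopsy. The steroid, T2/FLAIR, clinical, new-lesion and confirmation conditions also filter. This stands, which is why the pooled range is only an illustration.

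**A rule may exist elsewhere.** The SAP refers to an Integrated Summary of Efficacy SAP that was not available for this review, and investigators who know of the surgery may discount it. Neither cures the stated rule: the SAP adopts the investigator's call, and neither document tells the investigator how to treat a resection. Section 11.2 says how to measure around a surgical cavity but does not change the reference.

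**Censoring might remove it.** SAP Section 3 censors at the start of other anticancer treatment. If the planned resection counted, a response first seen at week 8 would fall after censoring. The SAP does not say whether it counts. If it did, Arms C and E would be censored before their first scheduled response scan, so either reading needs a sentence.

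**Disease control rate (DCR).** A reader might infer that DCR is inflated too. The supplied text does not define DCR. If it counts stable disease, moving a patient from stable disease to PR leaves it unchanged.

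**Progression-free survival (PFS).** A reader might infer a bias in PFS in a known direction. The documents do not support one. Progression is judged from the best or smallest measurement (Sections 11.3.3 and 11.5). A post-operative reference scan could only lower that reference or leave it unchanged, so its absence cannot make size-based progression earlier. Only the labelling of the reference scan is at issue.

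**Consequence.** The protocol analyzes efficacy by arm, and Arms C and E are tissue arms without an interim analysis. The pooled column already mixes schedules and tumor populations. This limits the severity but does not remove the surgical contribution.

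**Conclusion.** The point holds as a possibility that the text leaves open. For PR, the reference is a scan before first dose and hence before the planned resection. For CR, the criterion is absolute, but a complete resection meets its size condition. Nothing in the two documents resets the reference or bars a surgical reduction, and the SAP carries the result into the Arm C and E rows and the All Patients column.

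The firm part of the size is the step per response given in the working; it rests on the planned arm sizes and on measurable disease throughout. Operated patients make up 13% (18/138) to 32% (30/94) of All Patients. On the assumed shares, a pooled ORR of 5% would read about 8–28%; if no resection produced a response, the effect is zero. Severity is minor to should-fix, because ORR is a secondary endpoint and no test attaches to the pooled column.

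**What to change.** In SAP Section 3:

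- **Table 2.3 and Table/Figure 2.4:** leave Arms C and E out of the All Patients column for ORR, BOR and DoR. Show their responses only in separately labelled descriptive rows, with a footnote that the reference scan precedes surgery.
- **DCR in Table 2.3:** use the same denominator, for consistency only.
- **Arm D:** apply the same rule if Arm C or E patients are added to an Arm D response analysis.
- **Censoring:** state whether the planned resection counts as other anticancer treatment.
- **Table/Figure 2.1:** add a footnote naming the reference scan used for progression in Arms C and E.

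Keep the All Treated set for the other analyses. The change is SAP wording and footnotes, with no new data or scans. The cost is a smaller pooled response denominator, 64–120 instead of 82–150, and a stated exception to the SAP's rule of one analysis set throughout.
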